An unpublished clinical trial conducted in India of Shoden® (CTRI/2020/10/028397) evaluated the PK of three withanolides (withanolide A, withaferin A, and withanoside IV) in 16 healthy adults, aged 18-45 years. All three withanolides were detected by LC-MRM-MS in plasma (data provided by Arjuna LTD under a NDA).⁷⁹ This study was limited in scope due to the dose (480 mg), which was higher than that used in clinical trials involving Shoden®,^{52,53,57} the lack of older participants, and the limited range of withanolides targeted.

E.3. LC-MS detection of withanolides

As part of ongoing research at the BENFRA Center, [name] and the BSR/PKCore at OHSU have been developing LC-MS methods of detecting withanolides in mouse plasma, which will be optimized for human plasma and urine as part of the study. Figure 2 demonstrates good separation for several of the withanolides that will be analyzed in this study.

F. RESEARCH DESIGN AND METHODS

F.1. Study design

The proposed study is a randomized, double-blind, crossover trial evaluating (a) the PK of withanolides, from two doses of a commercially available WS root and leaf extract (Shoden®), (b) safety and tolerability of these doses and (c) the feasibility of remotely measuring sleep- and stress-related outcomes in older adults. Participants will be randomized to one of two dose sequence groups. There will be two 4-week study periods separated by a 2- to 4-week washout period. During each study period, participants will attend a 13-hour baseline PK study visit and return for 24- and 48-hour blood and urine collections. After the 48-hour visit, they will continue taking Shoden® at the administered dose (240 or 480 mg) for four weeks, at which time they will return for a follow-up visit. A flow chart of the study is provided in Figure 3.

Study Design Diagram

[figure not shown]

Figure 3. Study design. *Mini Mental State Examination (MMSE); #Geriatric Depression Scale (GDS); *Biometrics: weight, height, body mass index (BMI), age, blood pressure, pulse rate, temperature; *Lab measures: complete blood count (CBC), comprehensive metabolic panel (CMP), urinalysis, and TSH; * REDCap surveys delivered to and completed by participants in the week prior to each PK visit and 4-Week Follow-Up Visit. §Safety assessment at study visits includes safety labs (CBC, CMP, TSH, testosterone, UA), GDS-15, ECG, and AE questionnaire.

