Randomization and blinding will be done by the OHSU research pharmacy. A single dose of Shoden® will be dispensed by the research pharmacy to a member of the study team just prior to the participant's baseline PK visit for each study period. Participants will receive two single administration doses of Shoden® (240 and 480 mg). The order in which they receive these doses will be random to prevent a tolerance effect. The OHSU Research Pharmacy will randomize participants to one of two dose sequence groups, stratified by sex. Participants will consume Shoden® in the presence of a study team member following baseline measurements in order to ensure adherence to the study protocol. Prior to the 48-hour visit for each study period, a 35-day supply of Shoden® (240 or 480 mg per day) will be dispensed to a study team member. Whenever the study intervention is dispensed, the OHSU research pharmacy will record the date, participant ID number, and dose for accountability.

H.2. Administration

A single dose (240 or 480 mg) of the study intervention will be administered in an outpatient setting at each baseline PK visit. The dose sequence will be randomized. The research pharmacy will dispense one dose of Shoden® to a member of the study team, who will provide it to the participant for oral consumption. At the 48-hour visit for each study period, participants will be given a 35-day supply of the study intervention.

H.3. Criteria for intervention discontinuation and stopping guidelines

Participants will be advised during the informed consent process that they have the right to permanently discontinue Shoden® and/or withdraw from the study at any time without negative repercussions. Participants will also be counseled during the consent process that they may be withdrawn from the study at the discretion of the Principal Investigator or designees. A participant may discontinue and/or withdraw and/or be withdrawn from the study for the following reasons:

Administrative:

- 1) Withdrawal of participant consent
- 2) Request of site investigator or designees
- 3) Request of primary care physician
- 4) Non-compliance
- 5) Protocol deviation
- 6) Premature termination of the study

Adverse event (AE)/experience:

- 1) Worsening of pre-existing disease
- 2) Intercurrent illness
- 3) Death
- 4) Major/clinically significant alteration in laboratory values or biometric assessments after beginning product

- 5) Other AE

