- 6) Other reasons concerning the participant's health or well-being

The study will be terminated if two participants terminate due to intervention-related serious adverse events. Severe adverse events will be reviewed immediately by the PI to determine if severity and relatedness warrant termination of the study (Section N).

I. SCREENING AND STUDY ACTIVITIES

A schedule of study visits and assessments is shown in Table 1.

I.1. Phone screening

Potential participants will be screened over the phone by the study team, prior to attending an in-person screening visit. An IRB-approved telephone script will be used. During the phone screen we will ask participants to self-report that they are not currently pregnant, breast feeding, or actively trying to conceive a child. The telephone screening will take approximately 10-15 minutes. Eligibility will be documented and potential participants that meet the eligibility criteria will be scheduled for a screening visit.

I.2. Consent process

To ensure full comprehension of all aspects of their participation in the study, all potential participants will be mailed or securely emailed a copy of the IRB approved consent form prior to their in-person screening visit. They will be instructed to review the form ahead of time but not to sign it until the visit. For participants with limited English proficiency a qualified interpreter will be present for screening, the consent discussion, and the subsequent study visits. As this study does not specifically target participants with limited English proficiency, the short consent form in the language needed will be submitted to the IRB prior to use. All in-person screening visits and consenting will occur in a CTRC outpatient room. At the in-person screening visit, a member of the study team will review the consent form and then assess their understanding by asking the participant to describe key points of the study (e.g., purpose of study, number of visits, length of study) before signing. After the participant signs the consent, screening assessments and baseline measurements will start. A copy of their signed consent form will be provided to each participant. To ensure ongoing consent, participants will be asked if they wish to continue their participation in the study at the beginning of every in-person study visit and phone visit.

I.3. Screening visit

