1.6. Four-Week Follow-Up Visit

Participants will be asked to fast for 10-12 hours, excluding water, the night before each four-week follow-up visit in order to collect fasting glucose as part of the CMP. A single blood sample (two teaspoons (10 ml)) and a urine sample will be collected to assess steady state plasma levels and excretion of WS compounds. Returned capsules will be counted to assess for adherence. Participants will have an ECG and blood and urine samples will be sent for safety labs (CBC, CMP, urinalysis, TSH, serum total testosterone, serum DHEA-S). The Geriatric Depression Scale-15 will be administered. At the four-week follow-up visit for the second study period, participants and investigators will be queried as to their perception of the dose sequence administered. This visit is expected to take 45-60 minutes.

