1.7. Final Phone Visit

Two weeks following the four-week follow-up visit for the second study period, participants will be telephoned to assess for delayed adverse events using interviews and a standardized multi-system adverse events questionnaire. The Geriatric Depression Scale-15 will be administered. Participants will be instructed to contact the study team if they become pregnant or father a child after they have completed the study.

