1.8. REDCap Surveys

Participants will be emailed a link to electronic surveys in REDCap at four time points during the study: during the week prior to each PK visit and during the week prior to each four-week follow-up visit. Participants will complete two surveys at each time point: Pittsburgh Sleep Quality Index (PSQI) and the Perceived Stress Scale (PSS).

I.9. Washout Period

The two study periods will be separated by a 2- to 4-week washout period where the participant will not take the study agent. If the washout period is longer than 21 days, participants will be called at two weeks to assess for delayed side effects.

I.10. Subject participation duration

Including the screening visit, a two to four-week washout period between doses, and an exit phone interview for adverse event monitoring, it will take participants 13 to 14 weeks to complete the study.

Table 1. Schedule of study visits and assessments.

	Screen	PK visit			2-week f/u	4-week f/u	Washout Period	PK visit			2-week f/u	4-week f/u	Final visit +2 weeks
Study Period		1			1	1		2			2	2	
Event	Clinic Visit	0 to 12h	24h	48h	Phone visit	Clinic visit		0 to 12h	24h	48h	Phone visit	Clinic visit	Phone visit
Informed consent	X												
Vitals and biometrics	X	X ⁺	X	X		X		X ⁺	X	X		X	
Health screening	X												
Electrocardiogram (ECG)	X	X [§]	X [°]			X		X [§]	X [°]			X	
CBC*, CMP*, TSH [^] , and UA*	X	X [^]	X [°]			X		X [^]	X [°]			X	
Serum testosterone		X				X		X				X	
Single dose of intervention		X						X					
Single-dose PK blood draws		X	X	X				X	X	X			
Issue 35-day supply of Shoden®				X [#]						X [#]			
Steady state PK blood draw						X						X	
12-hour urine collection		X						X					
Single urine collection		X [¶]	X	X		X		X [¶]	X	X		X	
Collect and count unused capsules						X						X	
Adverse events questionnaire		X [*]		X	X	X		X [*]		X	X	X	X
Cognitive screen (MMSE)	X												
Depression screen (GDS)	X	X [♦]			X	X		X			X	X	X
REDCap surveys		X [▼]				X [▼]		X [▼]				X [▼]	

f/u – follow-up

§ ECG collected prior to Shoden® administration and at 7 hours post-Shoden® administration

* CBC = Complete Blood Count with differential; CMP = Comprehensive Metabolic Panel; UA = Urinalysis

^ CMP collected prior to Shoden® administration and at 10-hours post-Shoden® administration

▲ TSH = Thyroid-stimulating hormone

This will take place at the 24-hour visit if 48-hour visit is eliminated, as described in Section I.4.

¶ Aliquot of baseline urine prior to administration of Shoden®

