★ Adverse events questionnaire administered at beginning and end of baseline visits

♦ If PK Visit 1 is ≥14 days since the screening visit

▼ REDCap surveys will be delivered to participants' email during the week prior to each study visit.

^ An ECG and CMP will be collected at the 24hr visit if the baseline visit was halted prior to the 7hr ECG and CMP being collected.

J. STUDY DURATION

Recruitment and data collection is expected to begin upon approval from the IRB and continue for nine months. We estimate a total of six months for final data analysis. Total estimated study duration is 21 months (Table 2).

Table 2. Study timeline.

Activity	Month																							
	1-3			4-6			7-9			10-12			13-15			16-18			19-21			22-24		
Characterization studies																								
Product quality control																								
LC/MS Method Optimization																								
Recruitment/enrollment																								
Data collection																								
Plasma/urine LC/MS analysis																								
PK data analysis/summary																								
Reports, manuscripts																								

K. DATA AND SPECIMENS

The principal investigator will oversee the management of the participants, intervention, and analysis, which will be carried out by the clinical investigators, research statistician, and research assistant. Data entry, quality control and preparation, and participant management will be ongoing throughout the study.

K.1. Data collection methods

The case report forms for this study include a telephone screening script, a medical history form, a cognitive screening questionnaire (Mini Mental State Examination), a mood screening questionnaire (Geriatric-Depression Scale-15), a stress questionnaire (Perceived Stress Scale (PSS)), a sleep questionnaire (Pittsburgh Sleep Quality Index (PSQI)), an adverse events questionnaire, and a 2-week follow-up phone script. Other data collection methods include administering an electrocardiogram, urine collection, and blood collection. The PSS and PSQI will be delivered to participants' emails via REDCap.

K.2. Handling of data and specimens

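### The only numeric stopping rule counts participants who leave because of a related serious adverse event, not participants who have one, so a late period 2 event may not count

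*Combined protocol and SAP*

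**What the plan says.** Section H.3 ends with two sentences on stopping the study. The first is the numeric rule: "The study will be terminated if two participants terminate due to intervention-related serious adverse events". The second gives the PI discretion: "Severe adverse events will be reviewed immediately by the PI to determine if severity and relatedness warrant termination of the study". No other numeric study-stopping threshold appears in H.3, Section N or elsewhere.

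For individuals, H.3 is permissive: "A participant may discontinue and/or withdraw and/or be withdrawn from the study for the following reasons". The reasons listed include death, a clinically significant change in laboratory values and any other adverse event. H.3 speaks there of discontinuing and withdrawing. It applies *terminate* to a participant only in the stopping rule and does not define it.

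On timing, F.1 states: "There will be two 4-week study periods separated by a 2- to 4-week washout period". At each four-week follow-up visit (I.6) safety labs and an ECG are done and "Returned capsules will be counted to assess for adherence". After period 2 one contact remains (I.7): "Two weeks following the four-week follow-up visit for the second study period, participants will be telephoned to assess for delayed adverse events".

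Section N defines SAEs by outcome, but spells the abbreviation out as severe adverse events. It separately calls any CTCAE grade 3 to 5 event severe. The stopping rule says *serious*, a word that Section N does not define.

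**The concern.** A numeric stopping rule exists so that the decision to stop does not rest on case-by-case judgement alone. Here the count depends on what is done administratively after the event. Two participants could have the same related serious event, and one would count because they were withdrawn while the other might not because they stayed in or had already finished dosing.

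This matters most at the end of period 2, where the plan itself looks for harm: end-of-period labs and ECG, then a call meant to pick up delayed adverse events. At that point there is no product left to discontinue and little participation left to withdraw from. Other participants may still have dosing ahead, including four weeks at 480 mg. Section C.2.3 supports that dose only by a study in which 16 participants took it once.

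**Working it through.** The protocol gives no operating characteristics for the stopping rule and no rate of related serious events, so there is no stated figure to reproduce. The check is a reading of the rule against the schedule.

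**Step 1. When does period 2 dosing end?** Inputs are the two four-week periods (F.1), the washout, and the call two weeks after the last clinic visit (I.7). F.1 and I.9 allow a washout of 2 to 4 weeks, while I.4.1 caps the gap before Baseline Visit 2 at three weeks. Ignoring the two or so days of PK sampling that open each period, and counting from first dose:

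- Period 2 four-week visit with the I.4.1 cap: 4 + 2 + 4 = week 10, to 4 + 3 + 4 = week 11.
- The same visit with the F.1 and I.9 upper limit: 4 + 4 + 4 = week 12.
- Final call: two weeks later, so week 12 to 13 under the cap, or week 14 at the longest.

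Under either washout limit, a stretch of two weeks follows that visit in which the participant is still in the study but has no product to stop.

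**Step 2. Does the rule count the event?** Reading H.3 literally:

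| Situation of a participant with a related serious event | Counted toward two? |
|---|---|
| Withdrawn because of it | Yes |
| Dies | Probably; death is a listed reason in H.3 |
| Event in period 1, washout or period 2, participant stays in | Not on the literal wording |
| First recognised at the period 2 four-week visit | Only if the participant is then formally withdrawn before the final call |
| First recognised at the final call | Doubtful; nothing is left to leave |

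The third row follows from the permissive wording on individual withdrawal. The last two follow from the schedule.

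**Step 3. Could others still be dosed?** I.10 says "it will take participants 13 to 14 weeks to complete the study", and Section J says "Recruitment and data collection is expected to begin upon approval from the IRB and continue for nine months". Nine months is about 9 × 52/12 = 39 weeks. The last participant could therefore enter as late as about week 39 − 14 = 25 to 39 − 13 = 26, so staggered entry fits the timeline. The documents do not say how entry will be spread. If all participants started together and kept to the same schedule, nobody would have dosing ahead when a late event was recognised. With staggered starts, somebody could.

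**Step 4. What else would catch the event?** H.3 requires immediate PI review of severe events. Section N requires prompt reporting of SAEs to the PI and clinician co-investigator, and marks grade 3 to 5 events for immediate IRB reporting. N.2 has the PI review adverse events in real time. These steps apply whether or not the participant leaves, but none of them adds to the count of two.

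**The case against.** The strongest reply is that the sentence following the rule already covers the risk. PI review can end the study after one event, with nobody leaving, so a late event would be seen and acted on. This largely stands, and it is why the point is minor. A reader might infer that late period 2 events would go unreviewed or that the study could not be stopped for them. The documents do not support that reading.

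Second, *terminate* can be read broadly. A participant is still in the study until the final call, so someone with an event at the period 2 four-week visit can be withdrawn and counted. That also stands, and it rules out the stronger claim that such events can never count. But the result then turns on whether someone records a withdrawal that changes nothing about exposure, and a stopping rule should not depend on that.

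Third, few events qualify. The Section N list is restricted to grave outcomes, an asymptomatic laboratory abnormality would not ordinarily meet it, and participants are told to contact staff about moderate or serious events, so a hospitalization need not wait for a visit. A missed event also matters only when the count is one short. All of this is fair.

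Fourth, no wording makes the count fully automatic, because relatedness is decided by the PI and co-investigators under N.1. This is true of the present rule and of the proposed one. The rewording removes the dependence on withdrawal; it does not remove judgement about cause.

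A reader might also want a probability that the rule is missed, or a number of participants still at risk when it is. The first needs an event rate and a withdrawal rate, and the second needs an enrolment pattern. The documents give none of these.

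**Conclusion.** The point holds in a narrow form and is minor. Followed exactly, the only numeric stopping rule can leave a related serious event uncounted because the participant did not leave, most clearly when the event is first recognised at or after the period 2 four-week visit. Only the numeric trigger is affected. Medical review, reporting and the PI's power to stop the study are intact.

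The conclusion rests on reading the undefined word *terminate* as leaving the study or product. For other participants to be affected, it also rests on the assumption that enrolment is staggered, which the timeline permits but the protocol does not state. No size beyond this can be given. The mismatch between *serious* in H.3 and the severe label in Section N is a labelling matter that would not merit a comment alone, but it touches the same rule and is best settled in the same edit.

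**What to change.** Replace the numeric sentence in H.3 with wording such as: *Stop the study once two participants have each had a serious adverse event judged intervention-related under Section N.1, with serious defined by the outcome-based list in Section N, at any time from first dose through the final phone visit, whether or not they discontinue product or withdraw.* Keep the threshold of two.

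In the same edit, label the outcome-based definition in Section N *serious* and keep *severe* for CTCAE grade 3 to 5. Let the PI-review sentence in H.3 cover both severe and serious events, so that the relabelling does not narrow that review.

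The cost is one reworded sentence, a small addition to the next and one changed label. No visit, test or data item is added. The downside is that the rule may be reached slightly earlier.

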1.4.1. Baseline Visit (0-12hr)

Visit Timing: For the first study period, Baseline Visit 1 will occur a minimum of three days after the screening visit to allow for review of laboratory results and scheduling of appropriate facilities. For the second study period, Baseline Visit 2 will occur a minimum of two weeks (and not more than three weeks) after the four-week follow-up visit for the first study period.

Sample collection: Participants will be asked to fast for 10-12 hours, excluding water, the night before each baseline visit in an attempt to standardize gastrointestinal transit time and minimize delayed absorption of the study intervention due to the presence of food. Participants will be reminded during the pre-visit reminder call to arrive at the visit well-hydrated to facilitate blood collections. Study staff will place a peripheral intravenous catheter in the participant's arm or hand to allow for serial plasma specimen collection. Prior to administration of Shoden®, a baseline plasma sample of two teaspoons (10 ml) will be collected through the catheter using a syringe and transferred immediately into a heparinized Vacutainer tube. The participant will then be administered two capsules of Shoden® (240 or 480 mg total) on an empty stomach in the presence of study staff to ensure compliance. Participants will be asked to abstain from food and drink (excluding water) for the first two hours following consumption of Shoden® capsules to allow for transition into the small intestine and absorption. If signs of hypoglycemia are present, participants will be allowed to consume a high glycemic food and monitored for improvement. Participants will be provided water at the visit and will be encouraged to drink four 16-ounce cups of water over the 12 hours to maintain good hydration status. Serial blood samples (two teaspoons (10 ml) per sample) will be collected through a peripheral intravenous catheter, at 15, 30, 45, 60, 90, 120, 150, 180, 210, 240, 300, 360, 540, and 720 minutes after dosing. A baseline urine sample and a 12-hour pooled urine collection will be obtained to measure excretion of WS metabolites.

Tolerability and safety: Participants' weight, height, body mass index, age, blood pressure, temperature, respiration rate, and pulse rate will be recorded at each study visit to monitor for adverse events and asymptomatic illnesses that may impact study results. Vitals will be collected at baseline, 7 hours post-Shoden administration, and at the end of each baseline visit. At the beginning of each baseline visit, participants will complete an electrocardiogram (ECG) and the Geriatric Depression Scale-15. Four teaspoons of blood (20 ml) will be collected for safety labs (CBC, CMP, urinalysis, TSH, serum total testosterone). ECG will be repeated 7 hours post-intervention to assess for cardiac changes. One teaspoon (5 ml) will be collected for a repeat CMP at 10 hours post-intervention to evaluate kidney and liver function. Participants will be interviewed and administered a standardized multi-system adverse events questionnaire at the beginning and end of each baseline visit. This visit is expected to take 13 hours a total of 175 mL of blood will be collected.

If the baseline CBC shows hemoglobin or hematocrit levels below what is recommended by the FDA for blood donation, the visit will be halted immediately. Participants will be asked to stay for 2.5 hours after the study agent has been administered to assess for acute side effects. Two and a half hours was chosen because common withanolides have reached their C_{MAX} by this time based on a previous PK study using Shoden®.⁸⁰ The end-of-visit adverse events questionnaire will be administered by phone and missed safety evaluations (7-hour ECG and vitals, 10-hour CMP, 12-hour vitals) will be collected at the 24-hour visit. After the 24-hour visit, the participant will be withdrawn from the study.

If study staff have difficulties collecting blood samples for any reason, the decision may be made to halt the visit. Participants will be asked to stay for 2.5 hours after the study agent has been administered to assess for acute side effects. If the visit ends before the 7-hour mark, the end-of-visit adverse events questionnaire will be administered by phone and missed safety evaluations (7-hour ECG and vitals, 10-hour CMP, 12-hour vitals) will be collected at the 24-hour visit. Participants will be allowed to remain on the study if difficulties with blood sample collection were the only reason for halting the study visit early.

I.4.2 24- and 48-Hour Visits

Participants will return at 24 hours and 48 hours for a single blood collection (two teaspoons (10 ml)) and urine collection. Vitals will be collected. A CMP and ECG may be collected at the 24-hour visit if the baseline visit was halted prior to 7 hours. At the 48-hour visit, the adverse events questionnaire will be administered as the baseline measure for the subsequent four-week period. After the 48-hour visit, participants will be issued a 35-day supply of the appropriate dose of Shoden® (240 or 480 mg), which they will begin taking before bed every day for four weeks. These visits are expected to take 20 minutes. After analyzing the plasma and urine samples for the first two participants, a determination will be made as to whether the 48-hour PK visit is needed for future participants. If no withanolides are detected in plasma or urine at 48-hours, this time point will be eliminated to avoid undue participant burden.

